Title	Neratinib and Capmatinib combination (phase Ib/II) in metastatic breast cancer and inflammatory breast cancer patients with abnormal HER-family and c-Met pathway activity as measured by the CELsignia Signaling Analysis Test
Protocol No.	2020-0198
Phase	Ib/II
IND Number:	159611
IND Sponsor	MD Anderson Cancer Center
Primary Objectives	
 Phase Ib: To determine maximum tolerated dose for use in the Phase II portion of the trial Phase II: To determine overall response rate (ORR: CR+PR)
Secondary Objectives	
 To further characterize the safety and tolerability of neratinib + capmatinib and of neratinib + capmatinib in combination with an aromatase inhibitor in ER+ MBC To determine clinical benefit rate: (CBR: CR + PR + SD \geq 24 weeks) To determine the duration of response To determine progression free survival (PFS) To determine 2 years overall survival (OS)
Exploratory Objectives	
 To determine the functional status of the HER2, c-Met, and EGFR pathways using the CELsignia test To determine the ORR, CBR, DOR, PFS, and OS for the sub-group of patients with metastatic inflammatory breast cancer and for the sub-group of patients with metastatic non-inflammatory breast cancer Assess response per molecular subtype, Hormone Receptor positive (ER and/or PR, HER2 negative) and Triple Negative Breast Cancer Assess genomic profile of cancers treated on study to explore potential mechanisms of response and resistance.
Treatment Regimen	Neratinib PO once daily and Capmatinib PO twice daily (all patients). Aromatase inhibitor PO daily +/- ovarian suppression for patients with ER+ breast cancer.

Study Design	
This is an open-label, phase Ib/II study of neratinib plus Capmatinib in patients with metastatic breast cancer and patients with metastatic IBC.
 
Phase 1b – Dose Escalation of Neratinib with Capmatinib
 
This phase of the study will employ the Bayesian optimal interval (BOIN) design with the 3+3 design run-in, to find the MTD. The BOIN design is implemented in a simple way similar to the traditional 3+3 design, but is more flexible and possesses superior operating characteristics that are comparable to those of the more complex model-based designs, such as the continual reassessment method (CRM). The maximum sample size for dose escalation is 18. Patients are treated in cohorts of 3, beginning with Neratinib PO dose level 1 (120 mg, Dose 1-7, 160 mg, through end of treatment, see Table 2) in combination with Capmatinib PO level 1 (400 mg, see Table 3), with a maximum of 12 patients per dose. The target toxicity rate for the maximum tolerable dose (MTD) is 25%.
 
Phase II
 
Phase II will be a prospective, open label, interventional study for patients with previously treated HER2-negative metastatic breast cancer or metastatic inflammatory breast cancer. Subjects receive Capmatinib in combination with Neratinib (including an AI for patients with ER+/HER2- breast cancer). The MTD determined during Phase 1b will be used.
 
This portion of the trial will be conducted to assess the overall response rate (ORR) for patients treated at the MTD. The target ORR will be 25%, with unacceptable ORR as 5%. We assess the ORR using the Bayesian optimal phase 2 (BOP2) design (Zhou, Lee and Yuan, 2017).
 
Up to an additional 29 evaluable subjects with measurable disease will be enrolled. An interim analysis will be performed when the number of enrolled patients reaches 15.

Number of Patients	Total: 47 patients
Number of Sites	1 site
Study Population	
Phase 1b: previously treated HER2-positive and HER2-negative, ER-positive and ER-negative metastatic and inflammatory breast cancer patients.
 
Phase II: previously treated HER2-negative, ER-positive and ER-negative metastatic and inflammatory breast cancer patients with abnormal HER-family and c-Met signaling tumors. The CELsignia Multi-Pathway (CELsignia MP) Test will characterize the subjects' HER-family and c-Met-driven signaling pathways as either hyperactive or normally active.

Study Endpoints	
Primary Endpoints:
 
 Safety The primary safety endpoint is to determine the safety, tolerability, and dose limiting toxicities (DLT) (Phase 1b) of the combination of Neratinib + Capmatinib in ER- MBC and of Neratinib + Capmatinib in combination with an aromatase inhibitor for ER+ MBC. Efficacy For the Phase 2 portion of the study, the primary efficacy endpoint is overall response rate (ORR), defined as the rate of patients who achieved partial response or complete response as the best response. All tumor response will be evaluated by RECIST 1.1 and measured by QIAC system, via research collaboration. 
Secondary Endpoint(s):
 
 Clinical benefit rate (CBR) Defined as the rate of patients who achieved complete response, partial response and stable disease for ≥ 24 weeks as the best response of treatment. Duration of response (DOR) DOR is defined as the period measured from the date of the first occurrence of a CR or PR (whichever status is recorded first) until the first date that progressive disease or death is documented. Patients who have not progressed and who have not died by the date of data cutoff for analysis will be censored at the time of last tumor assessment date. If tumor assessments were performed after the date of the first occurrence of a CR or PR showed different response, DOR will be censored at the date of the first occurrence of a CR or PR plus remaining stable response from that time point. Progression free survival (PFS) PFS is defined as the time between date of treatment start to the date of documented disease progression or death, whichever occurs first. Data from patients who have not experienced disease progression or death will be censored at the last tumor assessment date and known to be free of disease progression. Data from patients with no post-baseline tumor assessment will be censored at the treatment start date plus 1 day. 2 year overall survival (OS) 2 year OS definition: the proportion of patients in the study who are alive 2 years after enrollment on to the study 
Exploratory Endpoints:
 
 For exploratory purposes, ORR, CBR, DOR, PFS, and OS will also be analyzed separately for the sub-group of IBC patients and for the sub-group of advanced or metastatic non-IBC breast cancer patients. Assess response per molecular subtype, Hormone Receptor positive (ER and/or PR) and Triple Negative Breast Cancer Assess genomic profile of cancers treated on study to explore potential mechanisms of response and resistance.
------------------------	--

1.0 Background Information

1.1 Metastatic and Inflammatory Breast Cancer and Clinical Unmet Need

Targeting the HER family receptor tyrosine kinases (RTKs) with small molecule inhibitors or monoclonal antibodies has been a common therapeutic strategy against multiple cancers. In particular, over expression of HER2 in breast cancer has been targeted successfully by anti-HER2 agents like neratinib, trastuzumab, and pertuzumab (1-3). The use of these agents led to remarkable improvements in outcomes for patients with HER2 overexpressing breast cancer. However, HER2 overexpression as detected by IHC or FISH is limited to 15-20% of all breast cancers and to 40% of inflammatory breast cancer (IBC). Moreover, some clinical trials have also indicated a weak correlation between HER2 expression or amplification levels and HER2 targeted therapy benefit (4-5). In addition to HER2 expression and amplification, somatic mutations in HER2 have been identified in 1-4% of breast cancers, mostly in HER2 amplification-negative breast cancer (6). Bose et al. have shown that some of these HER2 mutations conferred resistance to the reversible HER2/EGFR TKI lapatinib, but were sensitive to the irreversible HER2/RGFR TKI neratinib when tested in breast cancer cell lines (7). They also examined the location of these mutations and found that majority of these mutations (68%) mapped to the kinase domain. Seven of the 13 HER2 somatic mutations they characterized were activating mutations that are likely true driver mutations. These findings by Bose and his colleagues indicate that breast tumors considered to be HER2-negative may still be “addicted” to HER2 signaling as a consequence of harboring HER2 activating mutations, and hence may be susceptible to select anti-HER2 agents.

Preclinical data have also shown that c-Met and other HER family signaling pathways also participate in extensive crosstalk that can drive cancer progression (8,9). c-Met is the cognate receptor for Hepatocyte Growth Factor (HGF). In breast cancer, c-Met and HGF overexpression correlates with poor outcomes (10). Lindemann et al reported c-Met overexpression in 25% of HER2-positive breast tumors, supporting the hypothesis that both HER2 and c-Met receptors could synergize in promoting tumor growth (11). Shattuck et al showed that c-Met contributes to trastuzumab resistance, and a subset of HER2-positive breast cancer patients may benefit from combined inhibition of both HER2 and MET (12).

Phase II trials with c-Met targeting therapeutics in combination with the HER1 (EGFR) inhibitor erlotinib showed promising results in progression-free survival (13). However, Phase III clinical trials in NSCLC using MET overexpression as an indicator for c-Met targeted therapy and trials enrolling unselected patients to receive combination c-Met/HER targeting treatment failed to demonstrate clinical efficacy (14). These disappointing results suggest that the current methodologies to identify patients likely to respond to these therapies are not effective. Hence an alternative approach may be to identify patients with dysfunctional c-Met signaling who may respond to existing therapies.

1.2 A need to develop a HER2 and c-Met Signaling Activity Test in the Clinic

To address this unmet need, Celularity developed a functional cellular analysis diagnostic platform, ‘CELsignia,’ to measure real-time cell signal transduction activity in living tumor cells

of individual cancer patients (15,16). This approach overcomes the limitations of static genetic analyses of fixed cells by determining whether the dynamic signaling activity of certain known oncogenic pathways is normal or abnormal and can be inhibited by a matching targeted therapy. The CELsignia platform quantifies specific dynamic signal transduction activities in a patient's tumor cells.

To elucidate the role of HER-family signaling and the involvement of c-Met signaling as a cancer driver, the CELsignia Multi-Pathway (MP) test was developed using an impedance biosensor and live cells derived from each patient's tumor. The CELsignia MP test measures ex vivo real-time live cell response to specific HER-family and c-Met agonists to diagnose breast tumors with hyperactive HER1, HER2, HER3, HER4, and c-Met signaling activity. This functional assay is being utilized to select HER2-negative breast cancer patients with abnormal HER2-driven signaling activity in their tumor specimens for treatment with neoadjuvant HER2 therapies in two trials. These early stage breast cancer patients will be treated with HER2 inhibitors in combination with chemotherapy cycles followed by surgery and then assessed for pathological complete response (17,18).

To determine the prevalence of abnormal HER-family and c-Met signaling in HER2-negative breast cancer patients, the CELsignia MP test evaluated fresh tumor samples from 79 HER2-negative breast cancer patients (19). Of these, 19 of 79 samples had both hyperactive c-Met signaling and at least one hyperactive signaling HER-family receptor. Using 6 of these tumor samples, the IC50 values of multiple pan-HER inhibitors and c-Met inhibitors was determined along with the efficacy of the combinations of each pan-HER inhibitor with each c-Met inhibitor (20). The IC50 values for these inhibitors obtained using the CELsignia MP test were comparable to those derived using cell-free methods. In drug efficacy studies, every combination of pan-HER and c-Met inhibitors provided comparably high (at least 80%) of inhibitory activity effect ex vivo (22). These results suggest the sub-group of HER2-negative breast cancer patients diagnosed with coincident hyperactive c-Met and ErbB signaling by the CELsignia MP test may respond to a pan-HER and c-MET inhibitor combination. Chou and Talalay analyses using the CELsignia MP test were performed to characterize the linkage between c-MET and HER-family dysfunctional signaling in order to determine whether combined c-Met and pan-HER inhibitors would act additively, synergistically, or antagonistically. The analysis revealed that the mechanism of pan-HER inhibitors and c-MET inhibitors are not mutually exclusive and that this inhibitor combination is synergistic. The synergistic activity of these two classes of drugs suggests that the threshold drug concentrations for efficacy when the drug combination is used is less than what is required when these inhibitors are used as single agents. Thus, lower doses of these inhibitors can likely be used in combination than when used as single agents without affecting efficacy.

Hence, we propose a trial wherein we will identify HER2-negative advanced breast cancer and inflammatory breast cancer patients with hyperactive c-Met/HER-family activation in the tumor using the CELx MP test and treating them with a combination of neratinib, an irreversible tyrosine kinase inhibitor of the ErbB family of receptors (epidermal growth factor receptor (EGFR)/HER1, HER2, and HER4) and Capmatinib, a tyrosine kinase inhibitor of c-Met.

CELsignia Platform

Patient cancer cells are first isolated from tumor tissue using Celularity's proprietary cell microenvironment technology. Dynamic cell signaling activity is then measured using these patient tumor cells with an impedance biosensor instrument. An impedance biosensor is an analytical platform that converts changes in cellular activity to a measurable electrical signal. This instrument measures dynamic changes in cell adhesion and morphology initiated by signal pathway activation or inhibition in live patient tumor cells.

To determine the activity of a specific signaling pathway, an activating agent specific to a pathway receptor is used to turn on the pathway and a corresponding inhibitory agent specific to the pathway receptor is used to turn signaling off. When signaling pathways are stimulated in this manner, adhesion molecules are affected and cause a change in the impedance measured in a well. By relying on the principle of detecting signaling pathway activity, tests can be developed for a range of disease types and targeted therapies that affect various cellular pathways.

CELsignia Multi-Pathway Signaling Activity Test

The CELsignia Multi-Pathway Test (MP) is a qualitative Laboratory Developed Test (LDT) that measures HER1/EGFR, HER2, HER3 and c-Met signaling activity in tumor cells obtained from patients previously diagnosed with HER2-negative breast cancer. Fresh tissue specimens obtained from a biopsy procedure are collected in a Celularity provided specimen collection kit at the clinical site and then delivered directly to Celularity's CLIA-certified and CAP-accredited laboratory where the test is performed, and the test report is issued.

The CELsignia MP Test incorporates the following steps:

- 1) Measures signaling driven by HER2 dimerization with HER1 and HER3 and by HER1, HER3, and c-Met homodimerization:
 - A. Contacts cells with HER3 ligand (NRG1), HER1 ligand (EGF), and c-Met ligand (HGF) to activate corresponding pathways.
 - B. Contacts cells with HER2 dimer-blocker
- 2) Quantifies amount of HER1, HER2, HER3, and c-Met signaling
- 3) Transforms quantitative result into a final qualitative result that characterizes the activity level of HER-family and c-Met signaling in the tested patient tumor cells as either normally active or hyperactive.

Celularity has completed analytical validation studies in accordance with applicable FDA guidance and Clinical and Laboratory Standards Institute (CLSI) standards in its CLIA/CAP certified laboratory to characterize the performance of the CELsignia MP test. A summary of the results is below:

Table 1. Results of Analytical Validation Studies for CELsignia MP Test

Performance Characteristics	Results
Analytical Precision (Qualitative)	
Analytical Sensitivity (95% CI)	95.8% - 100% (88/88)
Analytical Specificity (95% CI)	95.8% - 100% (88/88)
Detection Limits	
Limit of Blank	0.0020 cell attachment units
Limit of Detection	0.0099 cell attachment units
Limit of Quantification	0.1000 cell attachment units
Cut-Off Characterization	
HER2	250 signaling units
c-Met	

1.3 Co-activation of ER and HER2 pathway and need of co-inhibit.

Preclinical and clinical data suggest the possibility that tumors can alternate between ER and HER2 as the dominant pathway, with targeted therapy against one pathway causing reactivation of the other growth factor pathways. For example, more than 20% of ER positive breast cancers activate HER2 pathways by many ways including ERBB2 mutation, amplification, or biological activation noted in both pre-clinical and clinical settings (20-22). While the data on whether the HER2 inhibition will re-activate the ER dependency of cancers may not be well established, enough accumulated data supports the additional inhibition of ER to the proposed combination of HER2 and c-MET inhibition. Therefore, we will add aromatase inhibitor therapy to the proposed study combination for patients with ER positive breast cancer in our study.

2.0 Scientific/Medical Rationale

For previously treated metastatic breast cancer or IBC patients, the prognosis is poor, which may be due to untreated dysregulated pathways, such as HER2 and c-Met. For HER2-negative breast cancer patients diagnosed with dysregulated HER-family and c-Met signaling by the CELsignia MP test, there is a strong scientific basis for treating these patients with neratinib and capmatinib, which are designed to inhibit this dysregulated signaling activity. Of note, metastatic IBC harbors the worst clinical prognosis compared to any other breast cancers. Moreover, once it becomes resistant to first line therapy – the response rate to second or above lines of therapy is poor (5-10% by history).

The primary study endpoints are the safety and efficacy of the combination of capmatinib and neratinib. Overall Response Rate (ORR) is the primary efficacy endpoint. This endpoint is typically used to assess the activity of a drug or drug combination when treating a patient population believed to have a disease mechanism corresponding to the therapy's mechanism of action.

2.1 Rationale for Open-Label Study

Once there is clear response rate observed here, we will further conduct confirmatory phase II or phase III studies. However, given the rarity of advanced breast cancer with HER2 activity while not called as HER2 positive, IBC, and their well-established poor outcomes, we believe a single arm phase II is sufficient to offer a clinical signal of this novel combination therapy that will possibly offer new options to patients who are in desperate need of better treatment.

2.2 Rationale to Combine the Neratinib and Capmatinib in IBC with HER2 and c-Met Pathway Activity

We believe that utilizing the CELsignia MP test to identify patients with hyperactive HER-family/c-MET signaling pathways can identify the cancer driver in HER2-negative breast cancer patients that traditional IHC methodology may not detect. The linkage between c-MET and HER-family dysfunctional signaling has been established both by Celcuity and other researchers and further analysis by Celcuity revealed that the mechanism of pan-HER inhibitors and c-MET inhibitors are not mutually exclusive and that this inhibitor combination is synergistic.

Furthermore, the synergistic activity of these two classes of drugs suggests that the threshold drug concentrations for efficacy when the drug combination is used is less than what is required when these inhibitors are used as single agents. Thus, lower doses of these inhibitors can likely be used in combination than when used as single agents without affecting efficacy, as is proposed here. Therefore, we propose a phase Ib/II trial to study the combination of Neratinib and Capmatinib in HER2-negative advanced recurrent or metastatic breast cancer and inflammatory breast cancer patients whose tumors have hyperactive HER-family and c-Met signaling activity as determined by the CELx MP Test.

3.0 Objectives

3.1 Primary objective

- Phase Ib: To determine maximum tolerated dose for use in the Phase II portion of the trial
- Phase II: To determine overall response rate (ORR: CR+PR)

3.2 Secondary objectives

- To further characterize the safety and tolerability of neratinib + capmatinib in ER- MBC and of neratinib + capmatinib with Aromatase Inhibitor in ER+ MBC
- To determine clinical benefit rate: (CBR: CR + PR + SD \geq 24 weeks)
- To determine the duration of response
- To determine progression free survival (PFS)
- To determine 2 year overall survival (OS)

3.3 Exploratory Objectives

- To determine the functional status of the HER2, c-Met, and EGFR pathways using the CELsignia test

- To determine the ORR, CBR, DOR, PFS, and OS for the sub-group of patients with metastatic inflammatory breast cancer and for the sub-group of patients with metastatic non-inflammatory breast cancer
- Assess response per molecular subtype, Hormone Receptor (HR) positive (ER and/or PR), HER2 negative and Triple Negative Breast Cancer
- Assess genomic profile of cancers treated on study to explore potential mechanisms of response and resistance.

4.0 Study design

This is an open-label, phase Ib/II study of Neratinib plus Capmatinib in patients with metastatic breast cancer and metastatic IBC. In both phase Ib/II, patients with ER positive, breast cancer will also receive an aromatase inhibitor +/- ovarian suppression (for pre/peri menopausal patients).

4.1 Phase 1b – Dose Escalation of Neratinib with Capmatinib

This phase of the study will employ the Bayesian optimal interval (BOIN) design (Liu and Yuan, 2015 Yuan et al., 2016) (24, 25), with the 3+3 design run-in, to find the MTD. The BOIN design is implemented in a simple way similar to the traditional 3+3 design, but is more flexible and possesses superior operating characteristics that are comparable to those of the more complex model-based designs, such as the continual reassessment method (CRM) (Zhou et al., 2018) (26). The maximum sample size for dose escalation is 18. Patients are treated in cohorts of 3, beginning with Neratinib PO dose level 1 (120 mg, Dose 1-7, 160 mg, through end of treatment, see Table 2) in combination with Capmatinib PO level 1 (400 mg, see Table 3), with a maximum of 12 patients per dose. The target toxicity rate for the maximum tolerable dose (MTD) is 25%.

This trial was designed and will be conducted using the shiny app “BOIN” (BOIN V2.6.3.0) available at <http://www.trialdesign.org..> Further information about the design can be found in Section 13.

Table 2. Phase Ib Neratinib PO dose levels, in combination of Capmatinib PO.

Dose Level	1	2	3
Neratinib PO	120 mg, Dose 1-7, 160 mg, through end	120 mg, Dose 1-7, 160 mg, Dose 8-14, 200 mg, through end	120 mg, Dose 1-7, 160 mg, Dose 8-14, 240 mg, through end
Capmatinib PO	400 mg b.i.d.	400 mg b.i.d.	400 mg b.i.d.

Table 3 : Fallback Dose levels.

	Dose level -1	Dose level -2
Neratinib PO	120 mg, Dose 1-7, 160 mg, through end	120 mg, Dose 1-7, through end
Capmatinib PO	300 mg b.i.d.	200 mg b.i.d.

Note: dose reduction should be based on the worst toxicity demonstrated at the last dose.

Dose reduction below 200 mg is not allowed

This protocol will be monitored by IND Office and safety data will be reviewed by IND Office after all subjects in a given cohort have completed the DLT assessment period (Cycle 1 and 2, total 56 days) and the dose level for next cohort will be determined based on the results.

Prior to advancing/changing dose levels, a cohort summary will be completed and submitted to the IND Medical Monitor for review and approval.

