7.3 General Treatment Guidelines

If a toxicity is attributed to one of the study drugs, it may be held and the other drug(s) will still be given as scheduled. If a toxicity is not clearly linked to a single drug, then both neratinib and capmatinib may be held. The treating physician may withhold any of the drugs per their discretion and discussion with the principal investigator as needed to maintain patient safety while a toxicity is evaluated and treated. The drug should be resumed after appropriate toxicity management and dose reduced, if indicated as per Section 10 of the protocol.

Patients must receive at least 80% of the scheduled doses of each study medication to be considered evaluable for DLT. Patients with ER+ breast cancer must receive at least 80% of the scheduled dose of AI to be considered evaluable for DLT. However, any patient who experiences DLT, will be counted as a DLT regardless of how many doses received.

As study therapy is given continuously, missed days of treatment will not be made up. A cycle is defined as 28 days regardless of the number of days of treatment received.

In the event the patient experiences intolerable side effect(s) attributed to the endocrine therapy agent(s), the treating physician may withhold the agent per their discretion and discussion with the principal investigator as needed to maintain patient safety while a toxicity is evaluated and treated. The treating physician may change the AI agent administered and prescribe treatment for symptom control, as clinically indicated.

The following delays are allowed except during the DLT assessment period:

- 1) Up to 4 weeks due to study related AEs
- 2) Up to 8 weeks due to non-study related AEs

Unanticipated Dose Interruptions:

Interruptions due to non-study related issues (logistical, natural disaster, etc) are permitted in the case of logistical reasons not related to study therapy, up to 2 cycles of study.

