10.2 Management of Diarrhea

Diarrhea is a commonly occurring toxicity. Monotherapy with neratinib has a median time of 3 days to onset of diarrhea. With combination therapy, it is anticipated that diarrhea may occur

earlier. For the majority of patients, diarrhea subsides after about 2 weeks. Therefore, intensive prophylactic measures begin at the start of therapy. If diarrhea occurs despite prophylaxis, treat with additional antidiarrheals, fluids and electrolytes as clinically indicated. Additionally, based on results from the CONTROL clinical trial, the neratinib dose will be escalated to the assigned target dose during the 1st cycle of treatment (29).

Patients **must** be instructed to:

- start prophylactic antidiarrheal therapy (see below) on day 1, with the first dose of neratinib
- continue prophylactic therapy as directed
- promptly report diarrhea symptoms
- record the number of stools per day
- record each dose of antidiarrheal medicine taken each day
- report constipation *before* taking any laxatives or stopping antidiarrheal medication. Anti-diarrheal medication may be held for constipation at the discretion of the treating physician, but should be resumed if diarrhea recurs.

Intensive primary prophylaxis

Antidiarrheal medication (loperamide) must begin with the first dose of neratinib. Patients must take an initial dose of loperamide 4 mg p.o. with the first dose of neratinib, then followed by 4 mg TID for the first 14 days. After two weeks on study, patients will take loperamide PO 4 mg twice a day (BID) for the remainder of the first two cycle of neratinib. Thereafter, loperamide will be administered as needed throughout neratinib treatment, not to exceed 16 mg per day.

Table 11: Suggested Dosing Time

	7am	2pm	7pm	9pm
C1D1 through 28 days	Neratinib & Capmatinib with food**		Capmatinib	
	Loperamide 4mg***	Loperamide 4mg***		Loperamide 4mg***

** Neratinib and Capmatinib dose will be as assigned

*** After the first 14 days, loperamide 4 mg is to be taken twice a day through the first two cycle only of therapy (Day 56). Daily dose as needed (not to exceed 16 mg per day) for Days 56+ (Cycle 3 and beyond).

For Grade 2 diarrhea lasting \geq 5 days despite prophylactic medication, and higher grade (Grade 3 and 4), we recommend following the guideline as noted in below Table 12.

Table 12: Management Guideline for Neratinib-related Diarrhea

Severity of Diarrhea*	Action

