
 Grade 1 diarrhea [increase of <4 stools per day over baseline] Grade 2 diarrhea [increase of 4–6 stools per day over baseline] lasting \leq 5 days Grade 3 diarrhea [increase of \geq 7 stools per day over baseline; incontinence; hospitalization indicated; limiting self-care activities of daily living] lasting \leq 2 days 	
 Adjust antidiarrheal treatment Diet modifications Fluid intake of ~2 L should be maintained to avoid dehydration Once event resolves to \leq Grade 1 or baseline, start loperamide 4 mg with each subsequent NERLYNX administration

 Any grade with complicated features[†] Grade 2 diarrhea lasting longer than 5 days[†] Grade 3 diarrhea lasting longer than 2 days[†] 	
 Interrupt NERLYNX treatment Diet modifications Fluid intake of ~2 L should be maintained to avoid dehydration If diarrhea resolves to Grade 0–1 in one week or less, then resume NERLYNX treatment at the same dose. If diarrhea resolves to Grade 0–1 in longer than one week, then resume NERLYNX treatment at reduced dose (see Table 2) Once event resolves to \leq Grade 1 or baseline, start loperamide 4 mg with each subsequent NERLYNX administration

 Grade 4 diarrhea [life-threatening consequences; urgent intervention indicated] 	
 Permanently discontinue NERLYNX treatment

 Diarrhea recurs to Grade 2 or higher at 120 mg per day 	
 Permanently discontinue NERLYNX treatment

Note: Antidiarrheal treatment adjustment will be per physician's discretion. Examples of antidiarrheal treatment include but not limited to:

- Diphenoxylate 5 mg/Atropine Sulfate 0.05 mg (Lomotil): 2 tablets or 10 mL by mouth, 4 times per day, as needed. Maximum 8 tablets, or 40 mL per day.
- Colestipol: 2 grams by mouth twice per day. Colestipol should be taken at least 1 hour after and at least 4 hours before other oral medications.
- Tincture of Opium, 10 mg/mL: 6 mg (0.6 mL) 4 times per day, as needed.

Note: If grade 3 diarrhea reoccurs, the patient may maintain the same dose level of Neratinib or have dose reduced to the next lower dose (120 mg is the lowest dose level of Neratinib), per physician discretion. The patient may voluntarily come off the study at any time.

* Per CTCAE v5.0

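### Table 12's permanent neratinib stop for recurrent Grade 2 or higher diarrhea at 120 mg is not limited to dose-reduced patients, although every dose level starts at 120 mg

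*Combined protocol and SAP*

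**What the plan says.** **Dose schedule.** Tables 2 and 3 in section 4.1 start all five levels (1, 2, 3, -1, -2) on neratinib 120 mg for doses 1-7. Level 3 is "120 mg, Dose 1-7, 160 mg, Dose 8-14, 240 mg, through end". Level -2 does not step up: "120 mg, Dose 1-7, through end".

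**Diarrhea rules.** Table 12 in section 10.2 has four rows that matter here:
- Row 1 covers Grade 1, Grade 2 for up to 5 days and Grade 3 for up to 2 days. Its leading action is "Adjust antidiarrheal treatment".
- Row 2 covers longer Grade 2 or Grade 3 episodes and any grade with complicated features. Neratinib is interrupted, then resumed at the same dose, or at a reduced dose if recovery takes more than a week.
- Row 3 stops neratinib permanently for Grade 4.
- The last row also stops it permanently, on the trigger "Diarrhea recurs to Grade 2 or higher at 120 mg per day".

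The sentence introducing the table reads, from its Grade 2 duration threshold on, "5 days despite prophylactic medication, and higher grade (Grade 3 and 4), we recommend following the guideline as noted in below Table 12". The Note below the table says "If grade 3 diarrhea reoccurs, the patient may maintain the same dose level of Neratinib" or be reduced at the physician's discretion, and adds that "120 mg is the lowest dose level of Neratinib".

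**DLT and evaluability.** Section 7.4 counts diarrhea as a DLT if Grade 2 lasts at least 5 days, if Grade 3 lasts at least 2 days, or at Grade 4. Section 7.3 states: "Patients must receive at least 80% of the scheduled doses of each study medication to be considered evaluable for DLT". A patient with a DLT counts whatever the dosing. Table 18 is indexed by evaluable patients.

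**The concern.** The last row has no duration condition and no exception for the step-up week. Its wording suits a patient who was reduced to 120 mg and relapsed there. It also fits a patient in week 1 who has not yet been escalated.

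Nothing says whether row 1 or the last row governs a second short Grade 2 episode at 120 mg. The introductory sentence does not settle it by keeping short episodes out of the table, because row 1 explicitly includes them.

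The main stake is patient handling. Neratinib could be withdrawn for good over events that the same table treats with antidiarrheals. At levels 1, 2, 3 and -1 a week-1 stop comes before the assigned dose is reached. Week 1 is relevant because section 10.2 gives a median of 3 days to diarrhea onset on neratinib alone and expects it may come earlier with the combination.

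The second stake is bookkeeping. A permanent stop for related toxicity could leave the DLT count altogether.

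**Working it through.** **1. The plan's own boundaries.** Inputs are the target φ = 0.25 (section 13.1) and the default alternatives (Appendix 1), taken as 0.6φ = 0.15 and 1.4φ = 0.35.
- Escalation: ln(0.85/0.75) / ln[(0.25 × 0.85)/(0.15 × 0.75)] = 0.1252/0.6360 = 0.1968; the plan states 0.197.
- De-escalation: ln(0.75/0.65) / ln[(0.35 × 0.75)/(0.25 × 0.65)] = 0.1431/0.4796 = 0.2984; the plan states 0.298.

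The Table 18 entries for 1 to 12 patients also reproduce, with the 3+3 run-in overriding the de-escalation entry at 3 patients. Table 18 is not in dispute; the question is who enters it.

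**2. A case that separates the rules.** Suppose Grade 2 diarrhea on days 2-3, resolved on day 4, and Grade 2 again on days 5-6, with no complicated features.

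| Rule | Result |
|---|---|
| Table 12, row 1 | Each episode lasts 2 days, within the 5-day limit: adjust antidiarrheals |
| Table 12, last row | Grade 2 has recurred at 120 mg: stop neratinib permanently |
| Section 7.4 | Neither episode reaches 5 days: no DLT |

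The clean case is recurrent Grade 2. For recurrent Grade 3 the Note lets the physician keep the dose, so the milder recurrence is the one without an explicit choice.

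**3. Evaluability.** The DLT window is 56 days (section 7.4) and neratinib is taken once daily, so 56 doses are scheduled.
- Required: 0.80 × 56 = 44.8, so 45 doses.
- Stop by dose 7: at most 7/56 = 12.5%, so non-evaluable.
- Level -2, where the row applies for all 56 days: 44/56 = 78.6% fails and 45/56 = 80.4% passes. Any non-DLT stop by dose 44 makes the patient non-evaluable.

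Section 7.3 does not name the period for the 80%; the 56-day window is the natural reading. Over cycle 1 alone, a week-1 stop gives 7/28 = 25%, which also fails.

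**4. Effect on the observed DLT rate.** Let p be the share of treated patients with a DLT and q the share stopped without one. The documents give no q; the values below are assumptions, with p = 0.25.

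| Handling of the stopped patient | Formula | q = 5% | q = 10% | q = 20% |
|---|---|---|---|---|
| Kept as non-DLT | p | 0.25 | 0.25 | 0.25 |
| Dropped (as written) | p/(1 - q) | 0.263 | 0.278 | 0.313 |
| Counted as DLT | p + q | 0.30 | 0.35 | 0.45 |

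**The case against.** **Intent and status.** The row most naturally describes the end of the reduction ladder: row 2 reduces the dose, the Note names 120 mg as the floor, and the last row says what happens on relapse there. On that reading the earlier prolonged episode, if within 56 days, is normally already a DLT under section 7.4 and counts whatever the dosing. Table 12 is a recommendation, and section 7.3 gives the treating physician discretion over withholding drugs. Outside level -2, the literal case needs onset, resolution and recurrence within seven doses, on loperamide 4 mg three times daily. All of this stands and makes the point small. It does not supply the missing restriction: a clinician following the row as printed would stop the drug.

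**A stronger reading.** A reader might infer that the plan understates toxicity and biases the MTD. The documents do not support that. The last table above shows that dropping the patient raises the observed rate compared with keeping the patient as a non-DLT. It lowers the rate only against a broader DLT definition that the plan does not use. Neratinib and capmatinib doses in week 1 are identical at levels 1-3, so week-1 stops cannot separate those levels. Nor is the stop hidden: Phase 1b records all adverse events (section 12.1.4), and the IND Medical Monitor approves dose changes (section 4.1).

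**Conclusion.** The point holds as a drafting fault in one row of Table 12. Applied as written, the row permanently stops neratinib for recurrent short Grade 2 diarrhea in the step-up week at every level, and throughout the DLT window at level -2. Row 1 treats the same episodes conservatively. Such a patient need not have a DLT, falls well short of 45 doses after a week-1 stop, and does not enter Table 18.

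The importance is minor. The conclusion rests on a literal reading of a recommended guideline whose likely intent is narrower, and on applying the 80% rule to the 56-day window. The documents give no frequency for the event, so neither a number of affected patients nor a change in MTD selection can be stated.

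**What to change.** Reword the last row of Table 12 so that it applies to diarrhea recurring to Grade 2 or higher at 120 mg per day after a dose reduction for diarrhea or, at level -2, after a row 2 interruption. Add that during step-up doses 1-7 all other rows apply, including permanent discontinuation for Grade 4.

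The cost is one table row and one sentence, with no extra patients. The downside is that some patients with repeated short Grade 2 diarrhea stay on neratinib with adjusted antidiarrheals instead of stopping. A few non-DLT stops could remain, for example at level -2 after a row 2 interruption for complicated features alone.

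No change to section 7.3 or 7.4 is proposed. Making toxicity-related dosing below 80% a DLT would widen the primary Phase 1b endpoint well beyond this ambiguity. For capmatinib, 0.80 × 112 = 89.6, so 90 doses are needed. A 12-day hold for Grade 2 creatinine under Table 15 leaves 112 - 24 = 88 and would become a DLT, although section 8.2.2 considers transient creatinine rises likely due to transporter inhibition.
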